### **9.2.3.1 Analysis**

Pairwise comparison as Cochran Mantel Haenszel test adjusted by surgical procedure will be applied to the proportion of patients who completed the study on Day 1, 2 and 3 with nausea between Day 1 and Day 3 defined in 1) of section 9.2.3.

## **9.2.4 Proportion of Patients with Vomiting on Days 1 through 3**

Vomiting will be as reported as an adverse event. The proportions described in section 9.2.3 will be calculated for vomiting.

### **9.2.4.1 Analysis**

The proportion will be analyzed in the same way as section 9.2.3.1.

## **9.2.5 Proportion of Patients Discharged by Day 10 who are Re-admitted for Any Reason Within 30 Days after Discharge from the Hospital**

The proportion of patients discharged by Day 10 who are re-admitted to the hospital for any reason will be calculated. Similarly, the proportion of patients discharged by Day 10 who are re-admitted to the hospital for Postoperative GI dysfunction-related causes will be also calculated.

### **9.2.5.1 Analysis**

Each proportion will be analyzed in the same way as described in section 9.2.2.1.

## **9.3 Exploratory Endpoints**

### **9.3.1 Time from the End of Surgery to Time to Discharge Readiness**

The time from the end of surgery to time to discharge readiness will be the hours between the date and time of surgery and the date and time of discharge readiness. The censoring will be defined in the same manner as defined for the primary endpoint.

#### **9.3.1.1 Analysis**

Treatment groups will be compared based on the time from the end of surgery to time to discharge readiness in the same way as described in section 9.1.1. A Kaplan-Meier curve will be provided by treatment group to make the comparison.

### **9.3.2 Time from the End of Surgery to Time to Actual Discharge from the Hospital (Length of Stay)**

The time from the end of surgery to time to actual discharge from the hospital will be the hours between the date and time of surgery and the date and time of actual discharge. The censoring will be defined in the same manner as defined for the primary endpoint.

#### **9.3.2.1 Analysis**

Treatment groups will be compared based on the time from the end of surgery to time to actual discharge from the hospital in the same way as described in section 9.1.1. A Kaplan-Meier curve will be provided by treatment group to make the comparison.

### **9.3.3 Proportion of Patients with Prolonged Hospital Stay due to GI Dysfunction**

The proportion of patients with prolonged hospital stay due to GI dysfunction for each treatment group will be calculated.

#### **9.3.3.1 Analysis**

The proportion will be analyzed in the same way as described in section 9.2.2.1.

### **9.3.4 Time from Initial Insertion of the Nasogastric Tube to Removal of the Nasogastric Tube**

The time from initial insertion of the nasogastric tube to removal will be calculated between these two time points for each patient, expressed in hours with two decimals. It will be summarized by treatment group.

#### **9.3.4.1 Analysis**

Summary statistics will be provided by treatment group. A pairwise comparison as ANCOVA adjusted by surgical procedure will be performed. Kaplan-Meier curves by treatment group for time to removal of the nasogastric tube from initial insertion will be provided.

### **9.3.5 Proportion of Patients with Abdominal Distension on Day 1 through the Day on which GI2 is Achieved**

Abdominal distension will be as reported as an adverse event. The following proportions in the mITT Population will be calculated.

- (1) The proportion of patients who achieved GI2 after Day 1
  - a) And who had abdominal distension on Day 1 through the day on which GI2 is achieved
  - b) And who had abdominal distension other than the time window above in a) from first dose to Day 10 or withdrawal or discharge day.
  - c) And who did not have abdominal distension
- (2) The proportion of patients who did not achieve GI2 after Day 1
  - a) And who had abdominal distension from first dose to Day 10 or withdrawal or discharge day
  - b) And who did not have abdominal distension

#### **9.3.5.1 Analysis**

Pairwise comparison as Cochran Mantel Haenszel test adjusted by surgical procedure will be applied to the proportion of patients who achieved GI2 after Day 1 and had abdominal distension on Day 1 through the day on which GI2 is achieved defined in (1) – a) of section 9.3.5.

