9.4.5.3 Exploratory Efficacy Endpoints

Exploratory efficacy endpoints will be as follows:

- Time from the end of surgery (as defined for the primary endpoint) to time to discharge readiness (defined as GI recovery based on the clinical judgment of the investigator)
- Time from the end of surgery (as defined for the primary endpoint) to time of actual discharge (departure) from the hospital
- Proportion of patients with prolonged hospital stay (defined as hospitalization for ≥ 7 days postoperatively) due to GI dysfunction
- Time from initial insertion of the nasogastric tube to removal of the nasogastric tube

- Proportion of patients with abdominal distention on Day 1 through the day on which GI2 is achieved
- Proportion of patients with nausea on Day 4 through day of discharge
- Proportion of patients with vomiting on Day 4 through day of discharge
- Proportion of patients who achieve GI2 in each treatment group by postoperative day
- Proportion of patients who receive concomitant medication that may have a laxative effect
- Effect of prior surgery (yes/no) on the GI2 endpoint

For time from the end of surgery to time to discharge readiness and to time of actual discharge from the hospital, the same KM approach as used for the primary efficacy analysis will be performed. The proportion of patients for each of the other parameters will be summarized by treatment group.

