## 6.2 Statistical Testing

All statistical tests will be performed at the 2-sided significance level of 0.05, unless otherwise noted. No multiplicity adjustment will be made in this study.

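### The abdominal distension test counts an event only in patients who also achieved GI2, so a difference in GI2 rates between arms can hide or reverse a difference in distension

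*SAP*

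**What the plan says.** Protocol 9.4.5.3 lists this as one of ten exploratory efficacy endpoints: "Proportion of patients with abdominal distention on Day 1 through the day on which GI2 is achieved". It does not limit the event to patients who achieve GI2, and it does not say where the window ends for those who do not. For this endpoint it asks for description only: "The proportion of patients for each of the other parameters will be summarized by treatment group".

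SAP 9.3.5 takes distension from adverse event reports and sets the denominator: "The following proportions in the mITT Population will be calculated". It then divides patients into two groups:

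- Group (1) achieved GI2 after Day 1. Cell (1)a holds those with distension from Day 1 through the GI2 day, (1)b those with distension only at other times, and (1)c those with none.
- Group (2) is "The proportion of patients who did not achieve GI2 after Day 1". Cell (2)a is defined as "And who had abdominal distension from first dose to Day 10 or withdrawal or discharge day", and (2)b holds those without distension.

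SAP 9.3.5.1 adds a test that the protocol did not ask for: a pairwise CMH test, adjusted for surgical procedure, on cell (1)a alone, that is, on the proportion of patients "who achieved GI2 after Day 1 and had abdominal distension on Day 1 through the day on which GI2 is achieved". Under SAP 6.2, "All statistical tests will be performed at the 2-sided significance level of 0.05, unless otherwise noted", with no multiplicity adjustment.

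**The concern.** GI2 is the primary endpoint and the outcome the drug is meant to improve. Membership of cell (1)a requires GI2 to have been achieved, so the tested event combines something favourable (recovery) with something unfavourable (distension). A patient who stays distended and does not reach GI2 falls in (2)a and, in the test, scores the same as a patient with no distension.

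An arm that brings more patients to GI2 puts more patients at risk of being a (1)a event. If distension among achievers does not fall enough to compensate, that arm looks worse, or no better, even when fewer of its patients were distended. At stake is the only distension comparison that carries a p-value.

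**Working it through.** The documents give no rate, power or sample size for distension, so there is no planned figure to reproduce. Protocol 9.2 assumes about 20% censoring within 240 hours in the sample size simulation, but gives no GI2 rate by arm. All rates below are assumptions.

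**Notation.** r = proportion achieving GI2; dA = distension rate in achievers; dN = distension rate in non-achievers.

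- Tested proportion, cell (1)a over mITT: r × dA
- All-patient proportion: r × dA + (1 − r) × dN
- Part left out of the test: (1 − r) × dN

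**A benefit hidden.** Placebo: r = 0.80, dA = 0.20, dN = 0.60. Drug: r = 0.92, dA = 0.18, dN = 0.50.

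- Tested: 0.80 × 0.20 = 16.0%; 0.92 × 0.18 = 16.6%
- Left out: 0.20 × 0.60 = 12.0%; 0.08 × 0.50 = 4.0%
- All patients: 16.0% + 12.0% = 28.0%; 16.6% + 4.0% = 20.6%

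The drug is better among achievers, among non-achievers and overall, yet the tested proportions show no benefit. To break even in the test, dA on drug would have to fall to 0.20 × 0.80/0.92 = 17.4%.

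**Other settings (arm A against arm B).**

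| r, A vs B | dA | dN | Tested, A vs B | All patients, A vs B |
|---|---|---|---|---|
| 90% vs 70% | 40% | 40% | 36% vs 28% | 40% vs 40% |
| 90% vs 70% | 30% | 60% | 27% vs 21% | 33% vs 39% |
| 90% vs 80% | 30% | 60% | 27% vs 24% | 33% vs 36% |
| 80% vs 80% | 30% | 60% | 24% vs 24% | 36% vs 36% |

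The first row shows a difference where none exists. With 50 per arm, A has 45 achievers, 18 counted events and 2 distended non-achievers not counted. B has 35, 14 and 6. Each arm has 20 distended patients. Rows two and three reverse the direction. In the last row r is equal, so recovery contributes nothing to the difference; a difference confined to non-achievers would still go uncounted.

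**Effect on the test.** Simulated two-sided 0.05 CMH test for the first row: 40,000 runs, no continuity correction, three strata assumed at 20/60/20.

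| mITT patients per arm | Rejects, as planned | Rejects, all patients |
|---|---|---|
| 44 | 12.6% | 4.8% |
| 50 | 13.1% | 5.2% |
| 85 | 19.7% | 5.0% |

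Nearly all of the planned test's rejections favour the arm with fewer recoveries.

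**Cell boundaries.** Taken literally, achieving GI2 after Day 1 places patients who reach it on Day 1 in group (2), so their Day 1 distension is not counted in the test either. Cell (2)a starts at first dose whereas (1)a starts on Day 1, and (2)a is not cut at GI2. Adding the two cells as written would therefore not give the protocol endpoint.

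**The case against.** The strongest reply is that little depends on this test. The endpoint is exploratory, the protocol asked only for a summary, and no primary or secondary conclusion uses it. The SAP tabulates (2)a and (2)b, so a careful reader can see the patients left out. This stands, and it limits the weight of the point; the table does not, however, correct the p-value.

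The size is also wholly assumed. In the first illustration the tested gap is 0.6 percentage points, about a third of a patient at 50 per arm, so it shows a masked benefit rather than a clear reversal. Even the all-patient gap of 28.0% against 20.6% would be detected with only about 13% power at 44 per arm and 20% at 85 (normal approximation, two-sided 0.05). That stands too.

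A reader might infer three stronger things that the documents do not support:

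- That better recovery always raises the tested rate. It does so only if distension among achievers does not fall enough to offset it.
- That everyone outside group (1) failed to recover. On a literal reading group (2) also holds Day 1 achievers, the fastest recoverers.
- That the protocol fixes a correct window for non-achievers which the SAP broke. The protocol leaves that end point open, so any end date has to be newly specified.

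The denominator could also be disputed. If it meant achievers only, the first illustration would give 20% against 18% with no reversal, but the comparison would then be conditional on a post-randomisation outcome. SAP 9.3.5 names the mITT Population, so the non-event reading is the natural one. SAP 5.1 could be read as requiring all three GI2 time components for mITT membership, which would remove many non-achievers, but SAP 9.3.5 itself expects mITT patients without GI2.

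**Conclusion.** The point holds for the tested comparison. With the mITT denominator, SAP 9.3.5.1 scores distended patients outside group (1) as having no event, and the tested quantity is the GI2 rate times the distension rate in achievers. It measures distension fairly between arms only if GI2 rates are similar, and the drug is intended to make them differ. The bias works against the arm with more recoveries, so it can conceal a benefit of active treatment as well as flatter a worse arm.

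The size is unknown. Under the assumed rates it ranges from nothing (equal GI2 rates), through a masked benefit (16.0% against 16.6% tested; 28.0% against 20.6% in all patients), to a reversed direction (27% against 21% tested; 33% against 39% in all patients). This is a minor, easily corrected flaw in an exploratory analysis. The descriptive cells, the other efficacy endpoints and the primary conclusion are unaffected.

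**What to change.** In SAP 9.3.5.1, apply the CMH test to one patient-level event with all mITT patients in the denominator:

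- For patients who achieve GI2, including on Day 1 or after discharge up to Day 10: any abdominal distension starting from Day 1 and ending with the day of GI2.
- For patients who do not achieve GI2: any abdominal distension starting from Day 1 and ending at the first of Day 10, withdrawal or discharge.

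Keep the (1) and (2) cells as description only, and state whether a Day 1 achiever belongs in group (1) or group (2).

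The cost is SAP wording and one small new derivation, settled before unblinding. The derivation is needed because (2)a as planned starts at first dose, so the event cannot be had by adding existing cells. No new data are required: distension comes from adverse event reports, which Protocol 8.3.1 collects through the End-of-study Visit, and Protocol 8.1.1.1 already follows the first bowel movement after discharge up to Day 10.

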### **9.3.6 Proportion of Patients with Nausea on Day 4 through Day of Discharge**

Nausea will be as reported as an adverse event. The following proportions will be calculated.

- (1) Proportion of patients who completed the study up to at least Day 4 with nausea occurring at least once between Day 4 and discharge
- (2) Proportion of patients who completed the study up to at least Day 4 without nausea occurring at any time between Day 4 and discharge
- (3) Proportion of patients who were discharged prior to Day 4

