8.3 Adverse Events and Serious Adverse Events

The definitions of an AE and an SAE can be found in [Appendix 3](#).

Adverse events reported by the patient (or, when applicable, by a caregiver, surrogate, or the patient's legally authorized representative) must be captured in source documents. Abnormal laboratory test results, blood pressure, pulse rate, and ECG findings after the first dose that are considered to demonstrate a clinically significant change from baseline will be recorded in the eCRF as treatment-emergent adverse events (TEAEs).

The investigator and any qualified designees are responsible for detecting, documenting, and recording events that meet the definition of an AE or SAE and remain responsible for following up AEs that are serious, considered related to the study treatment or study procedures, or caused the patient to discontinue study treatment or withdraw from the study (see [Section 7](#)).

8.3.1 Time Period and Frequency for Collecting Adverse Event and Serious Adverse Event Information

All AEs/SAEs will be collected from the date of signing of the ICF until the End-of-study Visit at the time points specified in the SoA ([Section 1.3](#)).

All SAEs will be recorded in the eCRF and reported to the CRO within 24 hours of awareness, as indicated in [Appendix 3](#). The investigator or qualified designee will submit any updated SAE information to the CRO within 24 hours of awareness.

The investigators or qualified designees are not obligated to actively seek AEs or SAEs after conclusion of the study participation. However, if the investigator or qualified designee learns of any SAE, including a death, at any time after a patient is no longer in the study, and the investigator or qualified designee considers the event to be reasonably

related to the study treatment or study participation, the investigator or qualified designee must promptly notify the CRO via phone, e-mail, or fax (see [Appendix 3](#)). Investigator assessment of causality must be included with all SAEs reported to the CRO. Serious adverse events with missing investigator causality will be followed up urgently until provided to the CRO.

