## 9. EFFICACY

Efficacy analyses will be performed for the mITT population unless otherwise specified.

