#### **9.3.6.1 Analysis**

Pairwise comparison as Cochran Mantel Haenszel test adjusted by surgical procedure will be applied to the proportion of patients who completed the study up to at least Day 4 with nausea occurring at least once between Day 4 and discharge defined in (1) of section 9.3.5.

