### **9.3.7 Proportion of Patients with Vomiting on Day 4 through Day of Discharge**

Vomiting will be as reported as an adverse event. The proportions described in section 9.3.6 will be calculated for vomiting.

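### SAP 9.3.6 and 9.3.7 count nausea and vomiting from Day 4 only until each patient's own discharge, over an unstated denominator, so the CMH test compares arms observed for different lengths of time

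*SAP*

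**What the plan says.** SAP 9.3.6 takes nausea from adverse event reports and lists three proportions. The first is the "Proportion of patients who completed the study up to at least Day 4 with nausea occurring at least once between Day 4 and discharge". The second is the same group without nausea. The third is the "Proportion of patients who were discharged prior to Day 4". No fixed end day is given.

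SAP 9.3.6.1 names the test: "Pairwise comparison as Cochran Mantel Haenszel test adjusted by surgical procedure will be applied to the proportion of patients who completed the study" to at least Day 4 with nausea. SAP 9.3.7 extends this to vomiting: "The proportions described in section 9.3.6 will be calculated for vomiting".

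The denominator of the first proportion is not stated. SAP section 9 sets a default: "Efficacy analyses will be performed for the mITT population unless otherwise specified". SAP 9.3.5, on abdominal distension, names its population outright: "The following proportions in the mITT Population will be calculated". SAP 9.3.6 does neither.

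Time to the discharge order is a secondary efficacy endpoint, and the study rationale (Protocol 2.1) links slow GI recovery to longer hospitalization. On data collection, Protocol 8.3.1 says: "All AEs/SAEs will be collected from the date of signing of the ICF until the End-of-study Visit".

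**The concern.** The length of the observation window is itself an outcome of treatment. A patient discharged on Day 5 has two days on which an event can count (Days 4 and 5). One still in hospital on Day 10 has seven. The CMH test adjusts for surgical procedure but not for time observed.

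Two arms with the same daily nausea risk can therefore give different proportions because one goes home sooner. The difference could be read as a separate benefit on nausea and vomiting when it only restates the discharge result. Nausea at home, a possible cost of early discharge, drops out of this endpoint.

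How far this goes depends on the denominator, and the SAP leaves that open.

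**Working it through.** **Figures in the plan.** None exist to reproduce here. The stated sample sizes (44 and 85 per group) are for the trend in RMST of GI2. The documents give no rate, effect size or power for nausea or vomiting from Day 4, and no length of stay.

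**Inputs from the documents.** Window from Day 4 to discharge (SAP 9.3.6); two-sided 0.05 with no multiplicity adjustment (SAP 6.2); about 50 to 85 per group (Protocol synopsis); planned GI2 difference of 24 h for 5 mg v placebo (SAP 4.2).

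**Assumed inputs.** Discharge time Weibull with shape 2.2; surgery ending at 14:00; mean discharge 120 h on placebo and 96 h on drug (the whole 24 h carried over to discharge); 10% daily nausea risk in both arms; counting capped at Day 10, which SAP 9.3.6 does not state. Strata are ignored.

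**Step 1: proportion with an event.** For discharge on day d, days at risk k = max(0, min(d, 10) − 3), and P(event) = 1 − 0.9^k. For d = 5 this is 1 − 0.9² = 19.0%. For d = 10 it is 1 − 0.9⁷ = 52.2%. Averaged over 2,000,000 simulated stays per arm:

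| Denominator | Placebo | Drug |
|---|---|---|
| All mITT | 19.2% | 12.4% |
| In hospital on Day 4 | 26.8% | 21.4% |

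Mean days at risk are 2.2 v 1.4. The implied share in hospital on Day 4 is 19.2/26.8 = 72% v 12.4/21.4 = 58%.

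**Step 2: false-positive rate, mITT denominator.** Two-proportion normal approximation.
- n = 50: pooled p = (0.192 + 0.124)/2 = 0.158. Null SE = √(2 × 0.158 × 0.842/50) = 0.0730, so the critical difference is 1.96 × 0.0730 = 0.143. Actual SE = √((0.192 × 0.808 + 0.124 × 0.876)/50) = 0.0726. Φ((0.068 − 0.143)/0.0726) = 0.151; adding the other tail (0.002) gives about 15%.
- n = 85: the SEs are 0.0560 and 0.0557. Φ((0.068 − 0.110)/0.0557) = 0.227; with the other tail, about 23%.

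**Step 3: in hospital on Day 4.** Of 50 randomized, 50 × 0.716 = 35.8 and 50 × 0.579 = 29.0 are analysed. Null SE = 0.107, critical difference 0.210, actual SE 0.106. Φ((0.054 − 0.210)/0.106) = 0.071; with the other tail (0.006), about 8%. At 85 randomized it is about 10%.

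**Step 4: sensitivity, mITT denominator.**
- Mean discharge 144 h v 120 h: 25.3% v 19.2%; about 11% and 16% at 50 and 85.
- Shift of 12 h (120 h v 108 h): about 7% and 9%.
- Shift of 6 h: about 5.5% and 6%.
- Daily risk 5% to 15%, with either pair of means 24 h apart: drug-to-placebo ratio 0.63 to 0.77.

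**Step 5: a second stay model.** Gamma stays, placebo mean 5 to 7 days, discharge 0.75 or 1 day earlier, daily risk 5% to 15%. The spurious difference is −2.7 to −9.1 points on mITT and −2.1 to −6.6 points among those in hospital on Day 4. The chance of a significant result favouring the drug (nominal 2.5%) is 6% to 18% at n = 44 and 8% to 31% at n = 85 on mITT. Among those in hospital on Day 4 it is 4% to 8% and 5% to 13%.

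**Step 6: direction.** Suppose half the patients are nausea-prone (daily risk 20% v 2%) and stay longer, placebo mean stay is 6 days, and only the low-risk half goes home a day earlier. Among those in hospital on Day 4, placebo shows 37.5% and drug 43.2%, so the drug looks worse. On mITT the figures are 29.1% v 28.5%.

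**Step 7: fixed window, Day 4 to Day 10.** With full reporting both arms give 1 − 0.9⁷ = 52.2%, a difference of zero. If only 25% of nausea at home is reported, the result is 29.1% v 24.4%, with rejection of about 8% and 10% at 50 and 85.

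**The case against.** Two stronger readings are tempting, and the documents support neither. A reader might infer that the SAP counts patients already home before Day 4 as event-free. It does not say so. It lists them as their own category, and the three lines can be read as mutually exclusive classes. The mITT default makes an all-mITT denominator the likelier reading. The wording also lets such a patient, who remains in the study until the End-of-study Visit, meet the description of reaching Day 4. That makes the denominator ambiguous; it does not settle it. A reader might also infer that the earlier-discharge arm must show less nausea. That is the tendency under mITT, but Step 6 shows that it can reverse among patients in hospital on Day 4.

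Other objections carry weight:
- The 24 h is a planned GI2 difference. Carrying all of it over to discharge is generous, and a smaller shift shrinks the bias quickly.
- Equal nausea risk with faster GI recovery is a strained null. GI2 itself requires no significant nausea or vomiting for 4 hours after solid food, so part of any observed difference could be real.
- Late nausea is not lost to the trial. SAP 10.1 tabulates all TEAEs by preferred term, and the proportion discharged before Day 4 is shown by arm.
- Daily contact after discharge up to Day 10 is specified only to record the first bowel movement (Protocol 8.1.1.1), so nausea at home may be under-reported.
- The window comes from the protocol's own endpoint definition.

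These points limit the size of the problem and the reach of the remedy. They do not make the observation times comparable.

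**Conclusion.** The point stands in this form: whatever the denominator, the tested proportion depends on how long each patient stays, and the test ignores that.

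On an mITT denominator, earlier discharge alone tends to lower the proportion. In the illustration it falls from 19.2% to 12.4%, with false-positive rates of about 15% and 23% at 50 and 85 per arm. On the in-hospital denominator the effect is smaller (26.8% v 21.4%; about 8% and 10%) and its direction is not assured. With a 12 h shift the mITT rates are about 7% and 9%.

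All sizes rest on assumed stays, a constant daily nausea risk that is equal between arms and at home, and the assumed carry-over to discharge. They show a range and are not predictions. Both endpoints are exploratory, and the primary conclusion is unaffected.

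**What to change.** 1. State the denominator of the first proportion in SAP 9.3.6, and the same for 9.3.7.
2. Apply the CMH test to the proportion of mITT patients with at least one nausea (or vomiting) AE from Day 4 through Day 10, regardless of discharge.
3. Record this in the SAP as a justified change from the protocol's definition, which ends on the day of discharge. Protocol 9.4 provides for such changes. Protocol 9.4.5.3 asks only for a summary of these proportions; the SAP added the test.
4. Keep the until-discharge proportions as a descriptive table beside the proportion discharged before Day 4.
5. Correct the cross-references: 9.3.6.1 points to item (1) of 9.3.5, and 9.3.7.1 to 9.3.5.1. Both concern abdominal distension.

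The cost is SAP wording and one derivation from AE dates that are already to be collected. The downside is that AEs at home may be reported less completely than in hospital, so the fixed window reduces the bias but may not remove it. The report should say so.
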